6.3.4 Dose modifications for elevated amylase and lipase

Event	Dose Modification Algorithm

Grade 2 elevation of amylase and lipase without symptoms of pancreatitis
	
Monitor amylase and lipase every other week, continue study therapy at the same dose level

Grade 2 elevation of amylase and lipase with symptoms of pancreatitis	Hold study therapy until both labs and symptoms are grade 1 or less. Consider restarting study therapy with a dose reduction if the patient is known to be deriving clinical benefit
Grade 3 elevation of amylase and lipase without symptoms of pancreatitis	Check amylase and lipase weekly until grade 2 or less, monitor for symptoms weekly (phone contact or visit) until grade 2 or less, and continue study therapy at the same dose level. Consider GI consultation.
Grade 3 elevation of amylase and lipase with symptoms of pancreatitis	Hold study therapy until both laboratory testing and symptoms are grade 1 or less. GI consultation is recommended. Consider restarting study therapy with a dose reduction if the patient is known to be deriving clinical benefit from treatment.
Grade 4 elevation of amylase and lipase without symptoms of pancreatitis	Hold study therapy until grade 2 or less, restart with one dose-level reduction if the patient is known to be deriving clinical benefit from treatment. GI consultation recommended.
Grade 4 elevation of amylase and lipase with symptoms of pancreatitis	Hold study therapy until both laboratory testing and symptoms are grade 1 or less. GI consultation is recommended. Consider restarting study therapy with a dose reduction if the patient is known to be deriving clinical benefit from treatment.

7. DRUG FORMULATION AND ADMINISTRATION

7.1 Everolimus

Everolimus will be provided by Novartis. Tablets are blister packed under aluminum foil in units of 10 tablets, which should be opened only at the time of administration, as everolimus is both hygroscopic and light sensitive.

7.1.1 Description

everolimus, an inhibitor of mTOR, is an antineoplastic agent. The chemical name of everolimus is (1R,9S,12S,15R,16E,18R,19R,21R,23S,24E,26E,28E,30S,32S,35R)-1,18-dihydroxy-12-[(1R)-2-[(1S,3R,4R)-4-(2-hydroxyethoxy)-3-methoxycyclohexyl]-1-methylethyl]-19,30-dimethoxy-15,17,21,23,29,35-hexamethyl-11,36-dioxa-4-azatricyclo[30.3.1.04,9]hexatriaconta-16,24, 26,28-tetraene-2,3,10,14,20-pentaone. The molecular formula is C53H83NO14 and the molecular weight is 958.2.

7.1.2 Form

Everolimus is supplied as tablets for oral administration containing 2.5 mg, 5 mg, 7.5 mg, and 10 mg of everolimus together with butylated hydroxytoluene, magnesium stearate, lactose monohydrate, hypromellose, crospovidone and lactose anhydrous as inactive ingredients. Everolimus 5 mg tablet is a white to slightly yellow elongated tablet with beveled edge and no score engraved with “5” on one side and “NVR” on the other. Everolimus 10 mg tablet is a white to slightly yellow elongated tablet with beveled edge and no score engraved with “UHE” on one side and “NVR” on the other side.

7.1.3 Storage and Stability

Store everolimus tablets at 25° C (77°F); excursions permitted between 15°–30°C (59°–86°F). Store in the original container, protect from light and moisture. Keep this and all drugs out of the reach of children. Everolimus is both hygroscopic and light-sensitive.

7.1.4 Handling

Qualified personnel, familiar with procedures that minimize undue exposure to themselves and the environment, should undertake the preparation, handling, and safe disposal of the chemotherapeutic agent in a self-contained and protective environment. Everolimus tablets should not be crushed. Direct contact of crushed tablets with the skin or mucous membranes should be avoided. If such contact occurs, wash thoroughly as outlined in the references. Study personnel should avoid exposure to crushed tablets.

7.1.5 Compatibility

N/A

7.1.6 Availability

Everolimus is considered an investigational agent in this study and will be supplied free-of-charge from Novartis.

7.1.7 Preparation

N/A

7.1.8 Administration

Patients will be instructed to take the everolimus in the morning, without food, at least one hour before or two hours after a meal, at the same time as the Pazopanib.

7.1.9 Ordering

Everolimus can be ordered from Novartis using a drug order form e-mailed to Novartis.

7.1.10 Accountability

All missed doses must be documented in the drug accountability log and the subject's medical record. Unused agent that is returned by subject is not held, but destroyed according to institutional policy. The investigator, or a responsible party designated by the investigator, must maintain a careful record of the inventory and disposition of the agent. This should be kept current and contain:

- Dates and quantities of investigational product received from Novartis
- Packaging lot numbers for product received
- Subject's identification
- Date and quantity of investigational product dispensed
- The initials of the dispenser

7.1.11 Destruction and Return

At the end of the study, unused supplies of everolimus should be destroyed according to institutional policies unless otherwise instructed by supplier Novartis. Destruction/return will be documented in the Drug Accountability Record Form.

7.2 Pazopanib

7.2.1 Description

Pazopanib, 5-[(4-[(2,3-Dimethyl-2H=indazol-6-yl)-2-pyrimidinyl]amino)-2-methylbenzenesulfonamide monohydrochloride, is an orally bioavailable angiogenesis inhibitor. Its molecular formula is C21H23N7O2S•HCl. Excipients in the tablet include microcrystalline cellulose, povidone, sodium starch glycolate, magnesium state, and a film-coat.

7.2.2 Form

Pazopanib monohydrochloride is supplied as a series of aqueous film-coated tablets containing 200mg and 400mg of the freebase:

- 200mg, oval-shaped, white, packaged in bottles containing 34 tablets each
- 400mg, oval-shaped, white, packaged in bottles containing 68 tablets each

7.2.3 Storage and Stability

Pazopanib 200mg and 400mg should be stored up to 25°C. Pazopanib has a 48 month shelf-life.

7.2.4 Handling

Qualified personnel, familiar with procedures that minimize undue exposure to themselves and the environment, should undertake the preparation, handling, and safe disposal of the chemotherapeutic agent in a self-contained and protective environment. Pazopanib tablets should not be crushed. Direct contact of crushed tablets with the skin or mucous membranes should be avoided. If such contact occurs, wash thoroughly as outlined in the references. Study personnel should avoid exposure to crushed tablets.

7.2.5 Compatibility

N/A

7.2.6 Availability

Pazopanib will be provided by GlaxoSmithKline free of charge.

7.2.7 Preparation

N/A

7.2.8 Administration

Patients will be instructed to take the Pazopanib in the morning, without food, at least one hour before or two hours after a meal, at the same time as the everolimus. The tablets should be swallowed whole and must not be crushed or broken.

7.2.9 Ordering

GlaxoSmithKline will ship labeled pazopanib bottles in a sealed carton (68 tabs per bottle for pazopanib 400mg and 34 tabs per bottle for pazopanib 200mg). A label will be affixed to each carton identifying the product, strength and number of bottles. In addition, a packing slip will be enclosed with the drug name, strength, lot/batch number, storage conditions, and expiration/retest date.

7.2.10 Accountability

All missed doses must be documented in the subject's medical record and patient diary. Unused agent that is returned by subject is not held, but destroyed according to institutional policy. The investigator, or a responsible party designated by the investigator, must maintain a careful record of the inventory and disposition of the agent. This should be kept current and contain:

- Dates and quantities of investigational product received from GlaxoSmithKline
- Packaging lot numbers for product received
- Subject's identification
- Date and quantity of investigational product dispensed
- The initials of the dispenser
- Dose preparation records

7.2.11 Destruction and Return

At the end of the study, unused supplies of Pazopanib should be destroyed according to institutional policies. Destruction will be documented in the Drug Accountability Record Form.

8. CORRELATIVE/SPECIAL STUDIES

8.1 Pharmacokinetic Studies

Phase I: Patients will have pharmacokinetic specimens drawn at 0, 1, 2, 4, 6 and 24 hours post-dose on cycle 1 days 1 and 15. If patients are treated on dose level -1, there will be a 48 hour blood draw (pre-dose) as well. Two samples will be drawn for each time point. Pharmacokinetic specimens should be collected as close to the indicated window as possible. Whole blood samples (2 mL) should be collected in EDTA vacutainers for everolimus pharmacokinetics. Whole blood samples for the determination of plasma pazopanib concentrations will be collected into separate 2mL EDTA vacutainers. The 24 hour pharmacokinetic specimen should be collected prior to drug dosing on day 2 and day 16. If patients are treated on dose level -1, there will be an additional 48-hour post-dose blood draw obtained prior to everolimus dose. In addition, two 2mL blood samples for everolimus and pazopanib concentration determination will be obtained cycle 2 day 1 and cycle 4 day 1.

Testing will be done on whole blood including plasma. See Appendices B and C for details on blood specimen procurement and shipping.

Expansion Cohort: Pharmacokinetic studies will not be performed in the expansion cohort

9. STUDY CALENDAR

Scans must be done ≤ 4 weeks prior to the start of therapy. In the event that the participant's condition is deteriorating, laboratory evaluations should be repeated within 48 hours prior to initiation of the next cycle of therapy.

All assessments must be performed prior to administration of any study medication. All study assessments and medications should be administered within ± 3 days of the protocol-specified date, unless otherwise noted.

9.1 Phase I:

		Treatment cycles			
	Screening ¹	Cycles 1, 2		Subsequent cycles	Off Study
		Day 1	Day 15	Day 1	
Informed Consent	X				
History	X	X	X	X	
Concurrent meds	X	X	X	X	
Physical exam (Ht, Wt, BSA)	X	X	X	X	X
Vital Signs	X	X	X	X	
Performance Status	X	X	X	X	X
CBC with differential/platelets	X	X	X	X	X
EKG	X	X	B		
Urinalysis, urine protein & creatinine ²	X	X		X	
Serum chemistry ³	X	X	X	X	X
Fasting Lipid Panel	X	X		X	X
Qualitative β-HCG ⁴	X	X		X	
Hepatitis B and C screen ⁵	X				
Pazopanib		X-----X			
Everolimus		X-----X			
Adverse event evaluation		X-----X		X	
Tumor measurements	X		A	A	X
Radiologic evaluation	X		A		X

1. Screening labs may be used as cycle 1 day 1 labs if performed within 7 days of initiation of study therapy.
 2. If UPC ≥ 1 then a 24 hour urine protein must be assessed.
 3: Albumin, alkaline phosphatase, total bilirubin, calcium, fasting glucose, LDH, phosphorus, total protein, SGOT [AST], SGPT [ALT], serum sodium, potassium, chloride, bicarbonate, BUN, magnesium, uric acid, amylase, lipase, thyroid stimulating hormone (day 1 of each cycle only).
 Monitor serum liver tests before initiation of treatment with pazopanib and at weeks 3, 5, 7 and 9. Thereafter, monitor at Month 3 and Month 4, and as clinically indicated. Periodic monitoring should continue after Month 4. Urine or serum pregnancy test (women of childbearing potential) at screening and day 1 of each cycle (+/- 3 days).
 5. Screening for hepatitis B : Prior to registrations, patients will be tested for hepatitis B viral load and serologic markers, HBV-DNA, HBsAg, HBs Ab, and HBc Ab. Patients with risk factors for hepatitis C should be tested using quantitative RNA-PCR

A. Tumor measurements should occur in the cycle 2 week 3, and every 2 cycles thereafter. Confirmatory scans should also be obtained 4 weeks following initial documentation of an objective response. If scans have been performed within 30 days before coming off treatment, they do not need to be repeated. If scans cannot be obtained (patients coming off treatment to go to hospice or have died), please document in study file.
 B. Pre-dose EKG obtained at baseline, cycle 1 days 1, 15, and cycle 2 day 1 only.

9.2 Expansion cohort

Test/Procedure	Screening		Treatment Cycles 1, 2 (28 day cycles)		Subsequent cycles (28 day cycles)	Off Study 28 days after last dose (+/- 7 days) ⁹	Survival
	-28 days	-14 days	Day 1 ¹ (±3 days)	Day 15 (±3 days)	Day 1 (±3 days)		
Informed Consent	X						
History	X		X	X	X	X	
Concurrent Medications	X		X	X	X	X	
Physical Exam	X		X	X	X	X	
Vital Signs		X	X	X	X	X	
Performance Status	X		X	X	X	X	
CBC with Differential/ Platelets		X	X	X	X	X	
Amylase and lipase		X	X		X		
EKG		X	X				
Urinalysis, Urine Protein & Creatinine ²		X	X		X	X	
Serum Chemistry ³		X	X	X	X	X	
TSH		X	X		X		
PT/INR, PTT		X					
HbA1c ⁷		X					
Fasting Lipid Panel		X	X		X	X	
Qualitative β-HCG ⁴		X	X				
Hepatitis B and C Screen ⁸		X					
Pazopanib			X-----X				
Everolimus			X-----X				
Adverse Event Evaluation			X-----X		X	X	
Radiologic Evaluation ^{5,6}	X				X	X	
Survival Follow-Up							X

1. Cycle 1 Day 1 evaluations are to be conducted within 1-week prior to start of protocol therapy. Screening labs may be used as Cycle 1 Day 1 labs if drawn within 7 days of initiating study therapy.
 2. If UPC ≥ 1, then a 24 hour urine protein must be assessed.
 3. Albumin, alkaline phosphatase, total bilirubin, calcium, fasting glucose, total protein, SGOT [AST], SGPT [ALT], serum sodium, potassium, chloride, bicarbonate, BUN, uric acid, magnesium, LDH, phosphorus
 4. Urine pregnancy test (women of childbearing potential) at screening and cycle 1 day 1 only.
 5. Radiological imaging should occur every 8 weeks, following cycle 1 day 1.
 6. If scans have been performed within 30 days before coming off treatment, they do not need to be repeated as an off-study assessment. If scans cannot be obtained (e.g. patients coming off treatment to go to hospice or patients have died), please document in study file.
 7. Applies to patients with uncontrolled diabetes mellitus
 8. Screening for hepatitis: Prior to registrations, all patients will be tested for hepatitis B serologic markers (HBsAg, HBs Ab, and HBc Ab, HBV-DNA) and for hepatitis C (using quantitative RNA-PCR)
 9. This visit can be foregone for patients who are too unwell to attend or for other reasons at the investigator's discretion. Patients may be contacted by phone to assess resolution of toxicities and may be contacted for survival follow up.

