3.3.8 Able to swallow oral medications

3.3.9 Resolution of any pre-existing toxicity from prior therapy to NCI CTCAE V4.0 grade 1 except neuropathy (\leq grade 2) and tinnitus (\leq grade 2), and hearing loss (\leq grade 4)

3.3.10 A female is eligible to enter and participate in this study if she is of:

3.3.10.1 Non-childbearing potential (i.e., physiologically incapable of becoming pregnant), including any female who has had:

- A hysterectomy
- A bilateral oophorectomy (ovariectomy)
- A bilateral tubal ligation
- Is post-menopausal

Subjects not using hormone replacement therapy (HRT) must have experienced total cessation of menses for \geq 1 year and be greater than 45 years in age, OR, in questionable cases, have a follicle stimulating hormone (FSH) value >40 mIU/mL and an estradiol value < 40 pg/mL (<140 pmol/L).

Subjects must discontinue HRT prior to study enrollment due to the potential for inhibition of CYP enzymes that metabolize estrogens and progestins. For most forms of HRT, at least 2-4 weeks must elapse between the cessation of HRT and determination of menopausal status; length of this interval depends on the type and dosage of HRT. If a female subject is determined not to be post-menopausal, they must use adequate contraception as defined immediately below during the trial and for 8 weeks after the last dose.

NOTE: Women are considered post-menopausal and not of child-bearing potential if they have had 12 months of natural (spontaneous) amenorrhea with an appropriate clinical profile (e.g. age appropriate, history of vasomotor symptoms) or have had surgical bilateral oophorectomy (with or without hysterectomy) or tubal ligation at least six weeks prior to randomization. In the case of oophorectomy alone, only when the reproductive status of the woman has been confirmed by follow up hormone level assessment is she considered not of child-bearing potential.

3.3.10.2 Childbearing potential, including any female who has had a negative serum pregnancy test within 2 weeks prior to the first dose of study treatment,

preferably as close to the first dose as possible, and agrees to use adequate contraception. Acceptable contraceptive methods, when used consistently and in accordance with both the product label and the instructions of the physician, are as follow:

- An intrauterine device with a documented failure rate of less than 1% per year.

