- Vasectomized partner who is sterile prior to the female subject's entry and is the sole sexual partner for that female.
- Double-barrier contraception (condom with spermicidal jelly, foam suppository, or film; diaphragm with spermicide; or male condom and diaphragm with spermicide).

Note: Oral contraceptives are not reliable due to potential drug-drug interactions.

3.3.10.3 A male with a female partner of childbearing potential is eligible to enter and participate in the study if he uses a barrier method of contraception or abstinence during the study and for 8 weeks after the end of treatment.

3.3.11 Subjects must provide written informed consent prior to performance of study-specific procedures or assessments, and must be willing to comply with treatment and follow-up. Procedures conducted as part of the subject's routine clinical management (e.g., blood count, imaging study) and obtained prior to signing of informed consent may be utilized for screening or baseline purposes provided these procedures are conducted as specified in the protocol.

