5.2 Pre-treatment Criteria

5.2.1 Screening evaluation

Within 28 days prior to start of treatment

- Complete physical examination
- Complete medical history and demographics
- Karnofsky or ECOG performance status
- Record concomitant medications
- Disease assessments: Baseline CT or MRI of the abdomen and pelvis and CT or X-ray of the chest. In patients with osseous lesions, bone X-rays and/or bone scans should be obtained.

Within 14 days prior to start of treatment

- Evaluation of vital signs including pulse, respiratory rate, body weight, and height
- Two blood pressure measurements should be taken at least 5 minutes apart
- Urine beta-HCG pregnancy test for women of childbearing potential
- Electrocardiogram

- Urinalysis, urine protein, and urine creatinine
- Laboratory assessments. Screening laboratory testing performed within 7 days of initiation of study therapy may be used for cycle 1 day 1.
 - Complete blood count with differential and platelets
 - Comprehensive Metabolic Panel including: sodium, potassium, chloride, bicarbonate, BUN, creatinine, calcium, alanine aminotransferase, aspartate aminotransferase, alkaline phosphatase, total bilirubin, albumin
 - Magnesium, phosphorus, LDH, amylase, lipase, thyroid stimulating hormone
 - Total cholesterol ≤ 300 mg/dL AND fasting triglycerides $\leq 2.5 \times$ institutional ULN.
 - Fasting lipid panel
 - Screening for hepatitis C (using quantitative RNA-PCR) and hepatitis B using serological markers (HBsAg, HBsAb, and HBCAb) for all patients.
 - Prothrombin time (PT) or international normalized ratio (INR) $\leq 2 \times$ institutional upper limit of normal (ULN) unless patients are on therapeutic anticoagulation with warfarin
 - Partial thromboplastin time (PTT) $\leq 1.5 \times$ institutional ULN unless patients are on therapeutic anticoagulation with warfarin

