5.2.1 Day 1 every cycle

The following will be undertaken prior to initiating study therapy and on day 1 of every subsequent cycle:

- Vital signs including blood pressure, pulse, respiratory rate and body weight. Height will be recorded on cycle 1, day 1 only.
- Karnofsky or ECOG performance status
- Complete physical examination and toxicity evaluation (CTCAE v 4.0)
- Update concomitant medications
- Complete blood count with differential and platelets
- Comprehensive Metabolic Panel: sodium, potassium, chloride, bicarbonate, BUN, creatinine, calcium, alanine aminotransferase, aspartate aminotransferase, alkaline phosphatase, total bilirubin, albumin
- Magnesium, phosphorous, LDH, amylase, lipase, thyroid stimulating hormone
- Fasting lipid panel
- Urine pregnancy test in women of childbearing potential (at screening and cycle 1 day 1 only)
- Urinalysis
- Urine protein & creatinine
- EKG (for cycles 1-2 only)

5.2.2 Cycles 1-2 day 15

The following will be undertaken day 15 of cycles 1 and 2:

- Vital signs including blood pressure, pulse, respiratory rate, body weight, and height
- Karnofsky or ECOG performance status
- Complete physical examination and toxicity evaluation (CTCAE v 4.0)
- Update concomitant medications
- Compete blood count with differential and platelets
- Comprehensive Metabolic Panel: sodium, potassium, chloride, bicarbonate, BUN, creatinine, calcium, alanine aminotransferase, aspartate aminotransferase, alkaline phosphatase, total bilirubin, albumin
- Magnesium, phosphorous, LDH

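### Pregnancy testing in the expansion cohort: no test is scheduled after cycle 1 day 1, and the calendar schedules urine where eligibility requires serum (minor, safety only)

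*Combined protocol and SAP*

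**What the plan says.** **Frequency.** The section 9.2 calendar, footnote 4, states "Urine pregnancy test (women of childbearing potential) at screening and cycle 1 day 1 only". The beta-HCG row has no mark under subsequent cycles or at the off-study visit. The day 1 list in section 5.2.1 opens with "The following will be undertaken prior to initiating study therapy and on day 1 of every subsequent cycle" and then limits this item: "Urine pregnancy test in women of childbearing potential (at screening and cycle 1 day 1 only". By contrast, the Phase I calendar in section 9.1 asks for "Urine or serum pregnancy test (women of childbearing potential) at screening and day 1 of each cycle".

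**Exposure and controls.** Both drugs are taken daily with no set number of cycles (5.3.1, 5.3.2, 5.6). Criterion 3.4.19 explains the exclusion of pregnant women by the drugs' teratogenic or abortifacient potential. Contraception is a condition of entry under 3.3.10.2. The accepted methods are "An intrauterine device with a documented failure rate of less than 1% per year", a vasectomized sole partner, or double barrier, and the same criterion warns that "Oral contraceptives are not reliable due to potential drug-drug interactions". The Pregnancy text in section 14.5 adds contraception advice up to 8 weeks after treatment, requires an on-treatment pregnancy to be reported within 24 hours of learning of it, and asks for newborn follow-up of at least 12 months.

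**Specimen.** Criterion 3.3.10.2 requires a "negative serum pregnancy test within 2 weeks prior to the first dose of study treatment". The screening list in section 5.2.1, for the 14 days before treatment, schedules a "Urine beta-HCG pregnancy test for women of childbearing potential".

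**The concern.** There are two separate points.

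First, if a woman conceives despite contraception, nothing in the schedule would show it. Detection would depend on history, examination, symptoms, or an incidental finding on the 8-weekly scan, while she continues two drugs that the protocol itself regards as potentially harmful to a fetus. The reporting rule in section 14.5 starts only once someone knows of the pregnancy.

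Second, a site that works from the calendar would collect urine and would not hold the serum result that the eligibility criterion demands.

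What is at stake is the safety of individual patients and the internal consistency of the schedule, not the inference on response.

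**Working it through.** The plan gives no figure to reproduce. The check is a comparison of texts and a simple count.

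**Step 1. The texts side by side**

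| Place | Applies to | Specimen | When |
|---|---|---|---|
| 3.3.10.2 | Expansion eligibility | Serum | Within 2 weeks before first dose |
| 5.2.1 Screening evaluation | Not limited to a cohort | Urine | Within 14 days before treatment |
| 5.2.1 Day 1 every cycle | Not limited to a cohort | Urine | Screening and cycle 1 day 1 only |
| 9.2 footnote 4 | Expansion | Urine | Screening and cycle 1 day 1 only |
| 9.1 footnotes | Phase I | Urine or serum | Screening and day 1 of each cycle |

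**Step 2. Frequency.** For the expansion cohort, 5.2.1 and 9.2 footnote 4 agree, so the cohort's schedule does not contradict itself here. The beta-HCG mark in 9.2 sits in the day 1 column shared by cycles 1 and 2 and could on its own suggest a cycle 2 test, but the footnote and 5.2.1 both rule that out. Section 9.1 differs. It covered dose level -1 (pazopanib 400 mg, everolimus 5 mg; section 5), which is the expansion dose (5.1). It is not a clean comparator, because the 5.2.1 list is not restricted to a cohort and so conflicts with 9.1 as well.

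**Step 3. Size of the gap.** Cycles last 28 days, so day 1 of cycle k falls on study day 1 + 28(k - 1). For a patient who starts C cycles, testing on the 9.1 pattern gives C day 1 tests and 9.2 gives 1. The number omitted is C - 1.

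- Stops in cycle 1: 1 - 1 = 0.
- Two cycles: 2 - 1 = 1 (day 29).
- Three cycles: 3 - 1 = 2 (days 29 and 57).
- Each further 28-day cycle adds 1.

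For scale, the Phase I update in section 2.3 says that 2 of 6 patients (2/6 = 33%) at the expansion dose stopped after 2 cycles for toxicity. A patient like that would miss one test.

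**Step 4. Specimen.** The timing agrees: 2 weeks is 14 days. The specimen does not. A negative urine test does not meet a criterion that asks for serum, so following the screening list and footnote 4 alone leaves 3.3.10.2 unmet.

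**Step 5. What catches the mismatch.** The opening of section 3.3 requires the investigator or a designee to review all baseline results that establish eligibility before enrollment. Section 4.2 requires the eligibility checklist to be completed and has the registrar validate eligibility. Either step would probably expose a missing serum result before treatment.

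**Step 6. Cost.** The 9.2 calendar already has urinalysis on day 1 of every cycle and blood tests at screening, so both specimens are already being collected.

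**The case against.** The strongest case against the first part is that it is a matter of preference. Two places state the same restricted schedule, which looks deliberate. The only comparator belongs to a dose-escalation part that is finished. Contraception is mandatory, oral contraceptives do not qualify, history, examination and adverse-event review take place on day 1 of every cycle, and nothing prevents a test when one is indicated. The population is older: the Phase I ages ran from 49 to 77, so there may be no woman of childbearing potential at all.

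Most of this stands, and it is why the point is minor. It does not remove the point. The controls lower the chance of pregnancy or act once it is suspected; none is a scheduled test. The age range does not settle the matter either: expansion eligibility starts at 18, and the post-menopausal rule requires at least a year without menses and age over 45, or hormone levels in doubtful cases.

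On the second part, one may say that a urine entry does not forbid a serum test and that the criterion governs entry. That is fair as to consequence. It does not make the schedule right.

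A reader might also try to project expected conceptions. The documents do not allow it: they give neither the number of women of childbearing potential nor a failure rate for double barrier. Nor can time at risk be taken from the Phase I urothelial durations (4, 4, 5.5 and 14 months). These are durations of stable disease or response, and section 2.3 places only 2 bladder cancer patients at the expansion dose, so at least two of the four appear to come from the higher starting dose.

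**Conclusion.** Both parts hold, as a cheap safety improvement of minor weight.

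1. The expansion schedule has no pregnancy test after cycle 1 day 1 under open-ended dosing. A reader might infer that the protocol contradicts itself for this cohort, or that it leaves women unprotected. Neither is supported: 5.2.1 and 9.2 agree, and contraception is mandatory. What is missing is scheduled detection.
2. The urine entry at screening is wrong against 3.3.10.2. A reader might infer that ineligible patients would be treated, and then removed from a response analysis restricted to eligible treated patients (14.1). That is conceivable, but the pre-enrollment checks make a late blood draw the likely consequence.

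The size is 0 omitted day 1 tests for a patient who stops in cycle 1, 1 after two cycles, and about one more per further cycle. The count takes day 1 testing in each cycle, as in 9.1, as its reference. The number of women affected is not stated and may be zero, so absolute risk cannot be quantified. No endpoint, sample size or error rate is touched.

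**What to change.** In one amendment, for women of childbearing potential:

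- **5.2.1, screening list:** change the test from urine to serum, within 14 days before the first dose, to match 3.3.10.2.
- **5.2.1, day 1 list:** replace the restriction to screening and cycle 1 day 1 with a urine test on day 1 of each cycle. This also brings the list into line with the testing frequency in 9.1.
- **9.2, footnote 4:** serum at screening, urine on day 1 of each cycle.
- **9.2, beta-HCG row:** mark the subsequent-cycles cell.

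The cost is four short text edits and a small charge per test. No visit or sample is added. The serum correction should be made whatever is decided about testing frequency.
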